5.4.2 Key secondary analysis

Kaplan-Meier estimates

For Duration of Response, an estimate of the survival function in each treatment group will be constructed using Kaplan-Meier (product-limit) method as implemented in PROC LIFETEST with METHOD=KM option. The PROC LIFETEST statement will use the option CONFTYPE=LOGLOG.

Median survival for each treatment group will be obtained along with 95% confidence intervals calculated from PROC LIFETEST output using the method of [\[Brookmeyer and](#)

[Crowley 1982]. Kaplan-Meier estimates of the survival function with 95% confidence intervals at specific time points will be summarized. The standard error of the Kaplan-Meier estimate will be calculated using Greenwood's formula [Collett 1994].

Treatment of ties

The ties = EFRON statement in LIFETEST procedure will be used to analyze time to event data with ties.

5.4.3 Audit-based BIRC assessment of PFS

Not applicable.

MedDRA	Medical Dictionary for Regulatory Activities
NCI	National Cancer Institute
NMQ	Novartis MedDRA queries
ORR	Overall Response Rate
OS	Overall Survival
PD-1	Programmed Death 1
PD-L1	Programmed Death-Ligand 1
pFBP	Proportion of subjects with a favorable biomarker profile
PFS	Progression-Free Survival
PR	Partial Response
PT	Preferred Term
RECIST	Response Evaluation Criteria in Solid Tumors
SAP	Statistical Analysis Plan
SD	Stable Disease
SMQ	Standardized MedDRA queries
TIL	Tumor Infiltrating T cells
ULN	Upper Limit of Normal
WHO	World Health Organization
WHO-DD	World Health Organization Drug Dictionary

1 Introduction

This statistical analysis plan (SAP) describes all planned analyses for the non-randomized section of the clinical study report (CSR), including the non-randomized single-arm 1A of CPDR001J2201. CPDR001J2201 is a randomized, open-label, phase II open platform study evaluating efficacy and safety of novel spartalizumab (PDR001) combinations in previously treated unresectable or metastatic melanoma. All planned analyses for the randomized section of the study are described in a separate analysis plan, referred as “main SAP for the randomized part of the study” in this document.

The content of this SAP is based on CPDR001J2201 protocol amendment version 05. All decisions regarding final analysis, as defined in the SAP document, have been made prior to database lock of the study data.

1.1 Study design

This is a randomized, open-label, multi-center, two-part, open platform phase II study to assess the efficacy and safety of the anti-PD-1 antibody spartalizumab in combination with novel agents in previously treated unresectable or metastatic melanoma.

A non-randomized single-arm (Arm 1A) has been added with protocol amendment 5 to assess the efficacy and safety of spartalizumab in combination with LAG525 in subjects with previously treated unresectable or metastatic LAG-3 positive melanoma, based on encouraging results from arm 1 following interim analysis 2 of the randomized section of the study.

This study consists of two parts, applicable for both randomized and non-randomized sections of the study :

- Part 1 : Selection phase
- Part 2 : Expansion phase

For more details on the design of the randomized part, refer to protocol or corresponding statistical analysis plan.

In the non-randomized section, arm 1A will enroll up to approximately 100 subjects in total with LAG-3 positive melanoma: 20 subjects in part 1 and up to approximately 80 subjects in part 2.

Study treatment in Arm 1A will be: LAG525 600 mg i.v. Q4W and spartalizumab 400 mg i.v. Q4W.

Two interim analyses for efficacy and futility will be conducted for arm1A: based on data from 20 subjects treated in Part 1 and from 20 additional subjects treated in part 2 (i.e. 40 subjects in total combined with part 1 subjects). The primary analysis will occur after all 100 subjects have been enrolled (combining part 1 and part 2) and followed for at least 9 months. The final analysis will be performed at the end of study (as defined in the protocol).

1.2 Study objectives and endpoints

The same objectives than for the randomized section of the study have been defined for the non-randomized section of the study. Refer to the main SAP for the randomized part of the study

for more details. [REDACTED]

2 Statistical methods

2.1 Data analysis general information

All analysis will be performed by Novartis. SAS version 9.4 or later software will be used to perform all data analyses and to generate tables, figures and listings.

Data included in the analysis

For each of the analyses, all statistical analyses will be performed using all data collected in the database up to the data cut-off date. All data with an assessment date or event start date (e.g. vital sign assessment date or start date of an adverse event) prior to or on the cut-off date will be included in the analysis. Any data collected beyond the cut-off date will not be included in the analysis and will not be used for any derivations.

All events with start date before or on the cut-off date and end date after the cut-off date will be reported as 'ongoing'. The same rule will be applied to events starting before or on the cut-off date and not having documented end date. This approach applies, in particular, to adverse event and concomitant medication reports. For these cases, the end date will not be imputed and therefore will not appear in the listings.

For Part 1, the interim analysis will be conducted once 20 patients enrolled in arm 1A have either completed two post-baseline tumor assessments or have discontinued the study treatment. For Part 2, if the arm 1A is expanded after interim analysis in part 1, the 2nd interim analysis will be performed once 40 patients (e.g. 20 in part 1 and 20 in part 2) have either completed two post-baseline tumor assessments or have discontinued the study treatment.

The cut-off date of the primary analysis of this non-randomized section will be determined once all patients from Part 2 are enrolled and followed for at least 9 months or have discontinued the study. The analysis cut-off for the final analysis will be established at the end of the study as defined in the protocol.

General analysis conventions

For information on general analysis conventions, see the main SAP for the randomized part of the study.

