1.1.3 Timing of interim analyses and design adaptations

The first interim analysis will be conducted in part 1 after approximately 10 subjects have been enrolled in each of the first three arms and have completed the second post-baseline tumor assessment or have discontinued study prior to completing the second post-baseline tumor assessment. The requirement to have at least 10 subjects in each arm is based on simulations showing that 10 is the minimal number of subjects to be able to declare futility as per decision rules presented below and also in Section 10.4.2 of the protocol. If more combination arms are added to the study via future protocol amendments, those combination arms would also have their 1st interim analysis after approximately 10 subjects have been enrolled. Timing of subsequent interim analyses for part 1 and statistical thresholds are further discussed in Section 4.2 of the protocol and Section 10.4.2 of the protocol, respectively. [13621010910464462Statistical_hypo](#)No interim analysis is planned for part 2.

Figure 1-1 presents pre-specified criteria for decision-making in the selection phase.

Figure 1-1 Pre-specified criteria for decision making at each decision point (interim analysis) in part 1 to determine expansion in part 2 or drop of a combination arm

[figure not shown]

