2.5.2 Statistical hypothesis, model, and method of analysis

Part 1: Selection Phase

No formal hypothesis testing will be conducted in part 1. The objective of this part of the study is to explore the anti-tumor activity of the combination of spartalizumab with novel agents as measured by ORR per RECIST v1.1, and to select an arm(s) with promising efficacy that will be advanced to the expansion phase.

To determine whether arms have the potential to demonstrate clinically meaningful response rates, arms will need to show that they cross a specific efficacy probability threshold during the selection phase to advance to the expansion phase. Conversely, arms can also be shown to cross a specific futility probability threshold and consequently will be declared as futile and enrollment in those arms will be terminated. These thresholds and probabilities are highlighted in Table 2-9.

Table 2-9 Probabilities thresholds used to declare efficacy or futility for an arm

Decision rule	Action
$P(\text{ORR} \leq 15\%) \geq 70\%$	Drop arm for futility
$P(\text{ORR} \geq 20\%) \geq 70\%$	Efficacy declared; Advance arm to expansion phase (part 2)

The futility decision rule was determined based on simulations such that arms with response rate that is not considered clinically meaningful (i.e. $\text{ORR} < 10\%$) will be dropped with high probability (as illustrated in Table 10-7 of the protocol). Similarly, the decision criterion for advancement to the expansion phase was determined so that arms with clinically meaningful response rate that warrants further development (i.e. $\text{ORR} > 25\%$) will be advanced with high probability ('power') (see also Table 10-7 of the protocol).

To calculate these probabilities, a beta-binomial posterior distribution will be used as shown below:

$$p_i \sim \text{beta}(y_i + 1, n_i - y_i + 1)$$

where y_i are the number of confirmed responses in a combination arm (i), and n_i are the number of subjects enrolled in a combination arm (i). In calculation of the posterior distribution, the uniform prior, Beta[1,1] will be taken into account for each arm. The posterior probability will be calculated separately for each arm based on the observed ORR based on RECIST v1.1 criteria at each decision point, i.e. at each interim analysis as described in Section 10.7 of the protocol.

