2.14 Interim analysis

Primary endpoint: Objective Response Rate (ORR)

Part 1: Selection phase

The 1st interim analysis is planned once at least ten patients have been randomized into each of the three initial treatment combination arms, and have completed at least 20 weeks of treatment (corresponding to two post-baseline assessments) or discontinued the study. It is possible to terminate one or more combination arms at the 1st interim analyses for lack of adequate efficacy, i.e. futility. It is also possible for advance one or more combination arms at the 1st interim analysis to the expansion phase if those arms cross a specific efficacy probability threshold.

Assessment of futility and efficacy will be based on the calculated Bayesian predictive probabilities of occurrence, using the following criteria highlighted in [Table 2-9](#).

The (posterior) predictive distribution of future responders conditioned on the observed data at the interim is a beta-binomial distribution. More details on the (posterior) predictive distribution used for this study are highlighted in [Section 2.5.2](#).

Enrollment and assessment at subsequent interim analyses for each treatment group will continue at an assessment period as defined in Section 4.2 of the protocol, or 45 subjects have been randomized into a treatment group rules presented in [Section 2.5.2](#).

Note: If new combination arms are added to the study, those combination arms will have their interim analyses at the same time-points as the first three combination arms on this study (after 10 patients have been randomized and have sufficient data for analysis, and then if needed, at an assessment period as defined in Section 4.2 of the protocol, or 45 patients have been randomized into each arm).

Part 2: Expansion phase

No formal interim analysis is planned for this part of the trial. The primary analysis will be performed once the expanded arm has fully enrolled and also after all patients randomized in the expansion phase had at least 9 months of follow-up. This timing would allow for a potential minimum duration of response of 6 months for all subjects randomized. Formal

hypothesis testing of the primary endpoint (as described in [Section 2.5.2](#)) will be performed at the primary analysis. The final analysis will be performed at the end of the study as described in [Section 2.5.1](#).

3 Sample size calculation

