2.5.2 Statistical hypothesis, model, and method of analysis

Part 1: Selection Phase

No formal hypothesis testing will be conducted in part 1. The objective of this part of the study is to explore the anti-tumor activity of the combination of spartalizumab with LAG525 agent in subjects with LAG-3 positive melanoma as measured by ORR per RECIST v1.1, and to expand this new arm if it shows promising efficacy.

To determine whether the arm has the potential to demonstrate clinically meaningful response rate, a specific efficacy probabilistic threshold should be met during the selection phase to advance to the expansion phase. If not, the arm will be declared as futile and won’t be expanded. These thresholds and probabilities are highlighted in [Table 2-2](#).

Table 2-2 Probabilities thresholds used to declare efficacy or futility for arm 1A

Decision rule	Action
$P(\text{ORR} \geq 20\%) \leq 70\%$	Drop arm for futility
$P(\text{ORR} \geq 20\%) > 70\%$	Efficacy signal - Consider advancing arm to expansion phase (part 2)

To calculate the posterior probabilities, a beta-binomial posterior distribution will be used as shown below:

$$p \sim \text{beta}(y + 1, n - y + 1)$$

Where y is the number of confirmed responses in arm 1A and n is the number of subjects treated. In calculation of the posterior distribution, uninformed prior Beta[1,1] will be taken into account. The posterior probability will be calculated based on the observed ORR using RECIST v1.1 criteria at interim analysis.

The final decision on whether the arm will be selected for advancement to the expansion phase will primarily be based on the observed ORR using decision rule described above but other efficacy (in particular duration of response), safety, and biomarker data will be considered as well. Novartis may decide to not expand the arm despite the efficacy probability threshold crossed.

With 20 treated patients, 5 or more responders need to be observed to meet the efficacy probabilistic threshold.

Part 2: Expansion Phase

If the pre-defined efficacy probabilistic threshold is met after the selection part, the arm 1A might be expanded.

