2.14 Interim analysis

Part 1 : Selection phase

As described in protocol amendment v05 Section 4.2.2, there will be one interim analysis planned for ORR once all patients treated in arm 1A have either completed two post-baseline tumor assessments or have discontinued study treatment.

Part 2: Expansion phase

A 2nd interim analysis will be conducted once 40 patients have been treated within selection and expansion phases and have either completed two post-baseline tumor assessments or have discontinued study treatment. The primary analysis of this non-randomized section of the study will be performed once all patients treated in arm 1A had at least 9 months of follow-up. This timing would allow for a potential minimum duration of response of 6 months for all subjects enrolled. Formal hypothesis testing of the primary endpoint (as described in [Section 2.6.2](#)) will be performed at this primary analysis. The final analysis will be performed at the end of the study as described in protocol Section 4.3.

3 Sample size calculation

Further discussion on sample size calculations can be found in Section 10.8.2 of the protocol.

4 Change to protocol specified analyses

Not applicable.

5 Appendix

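### Arm 1A's interim looks can count a response still awaiting confirmation as a failure, under a rule whose only alternative to advancing is futility

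*SAP*

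**What the plan says.** **Arm 1A SAP**

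- Timing: Section 2.1 places both looks when the subjects "have either completed two post-baseline tumor assessments or have discontinued the study treatment". Section 2.14 repeats this: "have either completed two post-baseline tumor assessments or have discontinued study treatment".
- Count: Section 2.5.2 defines the posterior as Beta(y + 1, n − y + 1): "Where y is the number of confirmed responses in arm 1A and n is the number of subjects treated".
- Decision: Table 2-2 drops the arm if P(ORR ≥ 20%) is 70% or less and considers advancing it otherwise. Section 2.5.2 gives the thresholds as 5 of 20 and 9 of 40.
- Cut-off: Section 2.1 states "Any data collected beyond the cut-off date will not be included in the analysis and will not be used for any derivations".
- Unconfirmed responses: under Section 2.5.1, a response that does not qualify as CR or PR becomes SD if seen more than 11 weeks in. Otherwise BOR is unknown, which the main SAP (Section 2.5.3, adopted by reference) treats as failure.

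**Main SAP (randomized arms)**

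- Section 2.5.2 also counts confirmed responses: the y terms "are the number of confirmed responses in a combination arm".
- Section 1.1.3 sets the first look when about 10 subjects per arm "have completed the second post-baseline tumor assessment or have discontinued study prior to completing the second post-baseline tumor assessment". Section 2.14 expresses the same point as subjects who "have completed at least 20 weeks of treatment (corresponding to two post-baseline assessments) or discontinued the study".
- Table 2-9 has separate futility and efficacy rules, with continued enrolment between them.

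Neither SAP says what to do with a response that is awaiting confirmation when an interim decision is taken.

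**The concern.** Two scans are enough to confirm a response seen at the first scan. They are not enough to confirm one first seen at the second scan, which needs a further assessment that the trigger does not require. In Arm 1A the same gap arises for a subject who responds at the first scan and stops treatment before the second. Such a subject adds 1 to n and 0 to y.

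In Arm 1A this can only lower the posterior probability, and missing the threshold means the arm is declared futile. An arm that has stopped enrolling is not restored by a confirmation a few weeks later. The primary analysis is not affected in this way, because it waits for at least 9 months of follow-up. The problem is confined to the interim looks.

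**Working it through.** **Inputs.** Beta(1,1) prior, the 20% and 70% cut-points, and thresholds of 5/20 and 9/40 (Arm 1A SAP, Section 2.5.2); the 15% and 20% rules (main SAP, Table 2-9). A true ORR of p = 25% is used for illustration; it is the target rate in the main SAP, Section 2.5.2. The share s of eventual confirmed responses still pending at the cut-off is an assumption, shown as a range.

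**Step 1. Reproduce the plan's thresholds.** P(ORR ≥ 20%) under Beta(y + 1, n − y + 1):

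| n | y | Probability | Decision |
|---|---|---|---|
| 20 | 4 | 0.586 | drop |
| 20 | 5 | 0.769 | advance |
| 40 | 8 | 0.562 | drop |
| 40 | 9 | 0.704 | continue enrolment |

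Both stated thresholds are reproduced, and one pending response reverses the decision at each. If a cohort of 20 has exactly 5 eventual confirmed responders, the chance that at least one is pending is 1 − (1 − s)^5: 41% at s = 10% and 67% at s = 20%.

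**Step 2. First Arm 1A look.** The counted response probability is q = p(1 − s). The chance of passing is P(X ≥ 5) with X ~ Bin(20, q).

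| s | q | Pass first look |
|---|---|---|
| 0 | 0.2500 | 58.5% |
| 5% | 0.2375 | 53.3% |
| 10% | 0.2250 | 48.0% |
| 20% | 0.2000 | 37.0% |

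**Step 3. Both Arm 1A looks.** Part 1 subjects reached the trigger before part 2 opened, so their pending responses are allowed to mature by the second look. Let X1 ~ Bin(20, q) be counted at look 1, M ~ Bin(20 − X1, (p − q)/(1 − q)) be part 1 responses that mature later, and X2 ~ Bin(20, q) be counted among the 20 new subjects. The arm passes both looks if X1 ≥ 5 and X1 + M + X2 ≥ 9. The result is 52.1% at s = 0, 41.7% at s = 10% and 31.3% at s = 20%.

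**Step 4. Randomized arm, first look at n = 10.** P(ORR ≤ 15%) is 0.833 with 0 responses (drop) and 0.508 with 1 (continue). P(ORR ≥ 20%) is 0.617 with 2 responses and 0.839 with 3 (advance). So 0/10 drops the arm, 1 or 2 continue it, and 3 or more advance it.

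| s | Drop (0) | Continue (1–2) | Advance (≥3) |
|---|---|---|---|
| 0 | 5.6% | 46.9% | 47.4% |
| 10% | 7.8% | 52.3% | 39.8% |
| 20% | 10.7% | 57.0% | 32.2% |

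At s = 10% advancement falls by 7.6 points: 2.2 go to futility and 5.4 to continuation.

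**The case against.** **The size of s is unknown.** This stands. A response at the first scan can be confirmed at the second. The look is set by the last subjects to qualify, so earlier subjects may already have a third scan. The share pending is therefore below the share of responses first seen at scan 2. The trigger is also a minimum, and the actual cut-off may fall later.

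**The decision is not purely mechanical.** Section 2.5.2 of the Arm 1A SAP also considers other efficacy, safety and biomarker data. However, the ORR rule is the primary basis, and the discretion spelled out is to decline expansion after a pass, not to continue after a miss.

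**A maturity rule may exist elsewhere.** Confirmation rules, interim timing and selection-phase execution are partly referred to the protocol and the SAP Technical Appendix, which are not at hand. The SAP's own explicit trigger contains no such rule.

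**Two stronger readings are not supported.** A reader might infer that the randomized arms suffer the same false futility. They do not: only 0/10 drops an arm at the first look, and most of the lost early efficacy is deferral to later looks (about every 20 weeks, up to 45 subjects), where pending responses can mature.

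A reader might also infer that the treatment-discontinuation trigger is itself wrong, since the main SAP waits for discontinuation of the study. But a subject who progresses at the first scan, stops treatment and enters survival follow-up may never have a second scan and has not left the study. Under the main SAP's wording the look could wait on that subject indefinitely. The Arm 1A trigger sets timing only, and scans after treatment stops still count if they precede the cut-off.

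**Conclusion.** The point holds for Arm 1A. Its interim rule requires confirmation, its trigger does not ensure that confirmation was possible, and its decision table offers nothing between advancing and futility. The resulting error can only work against the arm.

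At a true ORR of 25%, the cost at the first look is about 5 percentage points if 5% of eventual confirmed responses are pending, about 10 points at 10% and about 21 points at 20%. Over both looks it is about 10 and 21 points at 10% and 20%, with part 1 subjects matured by the second look. These figures rest on the assumed s and on independent binomial responses; they show sensitivity and are not estimates of what will occur.

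In the randomized arms the comparable harm is a rise in first-look futility from 5.6% to 7.8% or 10.7%. The change is worth making because it is cheap and removes a one-directional bias from a stated stopping rule.

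**What to change.** In Sections 2.5.2 and 2.14 of the Arm 1A SAP, add a hold. If the threshold is missed on confirmed responses but would be met were pending CRs and PRs counted, the futility decision waits. It waits until each subject with an unconfirmed CR or PR and no progression has had the next tumor assessment, progressed, died or left follow-up for tumor assessment. State that these assessments enter the held decision, since the cut-off rule would otherwise exclude them.

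Keep the treatment-discontinuation trigger, and say that the hold also covers subjects who stopped treatment with an unconfirmed response. Apply the same hold to the 0/10 futility rule in the main SAP. Efficacy decisions continue to need confirmed responses, so no threshold changes.

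The cost is a few lines of SAP text and, in borderline cases only, a delay of about one scan interval.
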